Health Search was founded in 1998 as a research unit of the Italian College of General Practitioners (SIMG). SIMG is a scientific society aimed to promote the role of General Practice within the National Health System. The main activities are focused on education and research. Research is mainly developed throughout the Health Search network, based on: (1) a school in which PCPs receive training and share the same standards for recording electronic patients' information; (2) a database (Health Search), where PCPs collect patients' information. The group working with HSD data is a multidisciplinary team of epidemiologists, statisticians and IT experts; it provides value-added services to: (1) the PCPs who contribute to the HSD; (2) the stakeholders that are interested in using this research tool. Health Search-SIMG is currently involved in several national and multinational research projects on drug safety and drug utilization, health technology assessment (HTA) and health services research studies.

The HSD collects longitudinal data from approximately 900 active GPs across Italy, with 700 of them selected as most reliable for research purposes. The HSD contains patient demographic information, medical data (e.g., diagnoses, tests and test results, hospitalization, etc.), drug prescription, and prevention information, collected when patients visit PCPs, from approximately 2.4 million patients, and one million active patients currently assisted by the GPs selected for research project participation. The current average length of patient's electronic medical records since inception of the database is approximately 10 years. A unique identification number links all data for an individual patient in an anonymous way and no identifying details are available. The geographical distribution of patients of these PCP is from 16 Italian regions and similar to the general Italian population, without significant

differences both in geographical location and age distribution (Prezioso et al., 2014; Masclee et al., 2013). The latest data currently available for research is data up to 31 December 2013.

The proposed database has been used in previous studies that also included similar European population-based primary care databases such as CPRD (Masclee et al., 2013).

Excluded Data Source: Local Health Units

A Local Health Unit (LHU) is a body assigned by the National Health System in Italy to provide healthcare to a specific geographic area, generally a province. The LHUs in Italy are responsible for assessing the medical needs and providing comprehensive care for a defined population. Each LHU is responsible for the hospital and primary care services in its area as well as for prevention and health promotion activities. LHUs have an information network that measures the expenditure for drug reimbursement for registered patients. LHUs record all claims from pharmacies concerning drugs that are fully or partially reimbursed. The data available include: demographics, hospital admission and discharge diagnoses, specialist visits, drug prescription and dispensation (primary care only), mortality, and costs. A patient's personal health number can be cross-checked with the registry office and hospital database. This allows the information to be connected to the date of birth, gender, and any record of previous hospitalisations. Diagnoses and procedures are recorded based on the International Classification of Diseases (ICD)-9 and ICD-9-CM codes. On average, each LHU covers a total population of 500,000 beneficiaries, and 3 to 5 LHUs have been included by [REDACTED] in previous studies. The main limitation of this database for our current study is its lack of primary care and specialist diagnosis records.

Excluded Data Source: Cegedim Longitudinal Patient Database

The CSD Medical Research group provides access to European longitudinal patient data using data collected from the electronic medical records entered into a primary care physician's software, including 700 GPs attending over 800,000 patients from Italy. CSD includes information on the patient profile, clinical profile, prescriptions and the prescriber profile, but no information on hospital admissions (date of admission, admission diagnosis, discharge diagnosis, hospital stay duration, accident, or emergency (A&E) visits or discharge status). Data characteristics are similar to those in the proposed database.

Data Source Excluded: Friuli Venezia Giulia Regional Information Health System (FVG)

FVG is in the northeastern part of Italy and has approximately 1.2 million inhabitants. In Italy, all citizens are covered by taxed-based public health insurance. The hospital discharge database of the FVG region of Italy routinely collects data from all hospitals in the region and includes information on patients' sociodemographic characteristics and treatment received during hospitalization. Given that the LHUs can capture the same data, in a larger population, this database was excluded.

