8.2. Operational Objectives

- To describe the characteristics of patients prescribed linaclotide at time of first prescription (defined as socio-demographics, comorbidities (up to 15), co-medications (up to 15), and other potential variables of interest (up to 10))
- To also describe characteristics of patients by specific subgroups of interest (e.g., paediatric population, elderly population patients with diabetes, hypertension, or cardiovascular disease diagnostic codes, patients with codes for constipation only)
- To estimate the number and percentage of patients with the potential for linaclotide off-label use in the following groups: off-label/abuse/excessive use as a laxative due to the pharmacology of linaclotide within patients with eating disorders; off-label use in other types of constipation disorders distinct from IBS-C, particularly in the elderly population; and potential for off-label use in the paediatric population for chronic constipation.
- To describe the proportion and characteristics of patients prescribed linaclotide (overall and by alleged indication) who experience any of the following:
 - o Discontinuation of linaclotide (permanently during the observation period)
 - o Switching from linaclotide to drugs potentially also used by patients with IBS-C moderate to severe: laxatives, antispasmodics, prokinetics, or antidepressants (Hugin, 2003)
- To describe the duration of linaclotide treatment until discontinuation or switching

- To describe the effect of the indication (IBS-C diagnosis versus other) on the time from initiation of linaclotide to discontinuation or switching

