9.3.4. IBS Diagnosis and Severity Definition

The target indication of linaclotide is the treatment of moderate to severe IBS-C in adults. There are several Read, ICD-9 or ICD-10 codes related to IBS, but none are specific to IBS-C. In order to identify potential cases of IBS-C patients using codes, a combination of an IBS code with a code for constipation will be used. Table 4, Table 5 and Table 6 in Annex 3 include a broad list of Read codes, ICD-10 and ICD-9 codes for the identification of patients with IBS with different level of specificity, and codes for constipation to be used in combination.

There are no Read, ICD-9, or ICD-10 codes to indicate the severity of IBS. The most studied and most commonly used tools for measuring IBS severity involve quality-of-life and patient-reported symptom metrics that are not routinely recorded in the computerised databases selected for this study. Some components like symptoms or number of healthcare visits (part of the Functional Bowel Disorder Severity Index [Drossman et al., 2011]) have been previously used in the development of an IBS severity measure. However, it is not envisaged that this will be done as part of this study.

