ANNEX 3. ADDITIONAL INFORMATION

A. Lists of Codes to Identify Patients with IBS and IBS Type

Table 4. Read Codes for the Identification of IBS and Constipation

Read Code	Description	Comments
J521000	IBS with diarrhoea	To be used as exclusion criteria
14CF.00	History of irritable bowel syndrome (IBS)	To identify potential prevalent cases
Eu45324	Psychogenic IBS	Unfrequently used, check for constipation
J521.00	Irritable colon–IBS	Preferred code, check for constipation
J521.13	Spastic colon	Unfrequently used, check for constipation
J521.11	IBS	Preferred code, check for constipation
19C..11	Constipation symptom	Preferred code, combined with IBS
19C..00	Constipation	Preferred code, combined with IBS
19C2.00	Constipated	Unfrequently used, combined with IBS
19CZ.00	Constipation NOS	Unfrequently used, combined with IBS
J520z00	Constipation NOS	Third choice, combined with IBS
J520.00	Constipation – functional	Second choice, combined with IBS
J520100	Chronic constipation with overflow	Unfrequently used, combined with IBS
J520000	Acute constipation	Unfrequently used, combined with IBS
J520200	Chronic constipation without overflow	Unfrequently used, combined with IBS
J520300	Drug induced constipation	Unfrequently used, combined with IBS
E264500	Psychogenic constipation	Unfrequently used, combined with IBS
J520y00	Other specified constipation	Unfrequently used, combined with IBS
1962.00	Colicky abdominal pain	Second choice as code in IBS
1971.00	Central abdominal pain	Third choice as code in IBS
1972.00	Epigastric pain	Third choice as code in IBS
196..00	Type of GIT pain	Unfrequently used
196..11	Abdominal pain type	Unfrequently used
1968.00	Abdominal discomfort	Third choice as code in IBS
1969.00	Abdominal pain	Second choice as code in IBS
197..13	Site of abdominal pain	Unfrequently used
197A.00	Generalised abdominal pain	Second choice as code in IBS
197C.00	Lower abdominal pain	Third choice as code in IBS
197Z.00	Site of GIT pain NOS	Unfrequently used
1963.00	Non-colicky abdominal pain	Unfrequently used
196Z.00	Type of GIT pain NOS	Unfrequently used
196..12	Type of GIT pain - symptom	Unfrequently used
1976.00	Right flank pain	Unfrequently used
1975.00	Left flank pain	Unfrequently used

197..11	Flank pain	Unfrequently used
197..12	Iliac fossa pain	Unfrequently used
1977.00	Right iliac fossa pain	Unfrequently used
1978.00	Left iliac fossa pain	Unfrequently used
197B.00	Upper abdominal pain	Unfrequently used
197D.00	Right upper quadrant pain	Unfrequently used

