4763.00	Faeces: mucous present	Unfrequently used
19EH.00	Mucus in faeces	Unfrequently used
198..00	Nausea	Second choice as code in IBS
1982.00	Nausea present	Unfrequently used
198..12	Nausea symptoms	Third choice as code in IBS
198..11	C/O - nausea	Unfrequently used
198Z.00	Nausea NOS	Unfrequently used
R070000	[D] Nausea	Unfrequently used
R070.00	[D] Nausea and vomiting	Unfrequently used
R093000	[D] Abdominal swelling	Unfrequently used
J16y411	Flatulent dyspepsia	Unfrequently used
19D..12	Anal symptoms	Unfrequently used
19D..11	Tenesmus symptom	Unfrequently used
19D..00	Tenesmus	Unfrequently used
19D2.00	Tenesmus present	Unfrequently used
19DZ.00	Tenesmus NOS	Unfrequently used
19E..11	Faeces symptom	Unfrequently used
19E..12	Motions – symptom	Unfrequently used
19E..00	Faeces/motions – symptoms	Unfrequently used
19F..	Diarrhoea symptoms	
19G..00	Diarrhoea and vomiting	
J525.00	Functional diarrhoea	
J43z.	Chronic diarrhoea	
J4z..	Non-infectious diarrhoea	

Abbreviations: IBS=irritable bowel syndrome; IBS-C=IBS predominately with constipation; NOS=unspecified

Patients with IBS will be identified through the following criteria:

- One or more IBS- related codes among the following: J521.00, J521.11, J521.13, Eu45324, 14CF.00.
- Alternatively, a combination of a code of abdominal pain or discomfort (in gray background and regular font) and at least two codes among those reported as “second choice as code in IBS”, “third choice as code in IBS” or “unfrequently used” (in *italics* and gray background).

Patients with only 14CF.00 will identify as prevalent IBS-C patients since the diagnosis date is uncertain.

Patients with IBS-C will be identified through the following criteria:

- Patient with IBS as specified above and one preferred code including the term “constipation”

Patients with IBS and a code for diarrhoea will be IBS-D. Patients with IBS only or meeting both criteria will be IBS-M.

Table 5. ICD-10 Codes for the Identification of IBS and Constipation

ICD-10 Code	Description	Comments
K58	Irritable bowel syndrome (IBS), irritable colon	Preferred code, check for constipation
K58.0	IBS with diarrhoea	To be used as exclusion criteria
K58.9	IBS without diarrhoea; IBS NOS	Preferred code, check for constipation
K59.9	Functional intestinal disorder, unspecified	Not specific
K59.0*	Constipation	To be used in combination with K58, K58.9, and K59.9 to identify IBS predominantly with constipation (IBS-C)

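### The UK definition of IBS-C contradicts itself: Table 4 and section 9.3.4 admit 12 constipation codes, including drug-induced constipation, while the criterion under Table 4 admits two

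*Protocol*

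**What the plan says.** Section 9.3.4 notes that no available code is specific to IBS-C, so that "a combination of an IBS code with a code for constipation will be used". It refers to Annex 3 for the codes and does not limit which constipation codes count.

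Table 4 in Annex 3.A (the UK Read codes) lists 12 constipation codes, each with a comment that it is to be combined with IBS. Two carry the comment "Preferred code, combined with IBS". The entry "Drug induced constipation" (J520300) and the entry for acute constipation (J520000) are among those with the comment "Unfrequently used, combined with IBS".

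The criteria printed under the table are narrower. IBS-C is defined there as "Patient with IBS as specified above and one preferred code including the term" constipation. For the remainder, "Patients with IBS only or meeting both criteria will be IBS-M". A separate line states: "Patients with only 14CF.00 will identify as prevalent IBS-C patients since the diagnosis date is uncertain".

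One of the objectives in section 8.2 is to count potential "off-label use in other types of constipation disorders distinct from IBS-C, particularly in the elderly population". Section 9.7.1 sets two relevant subgroups: non-IBS-C patients with chronic constipation, and patients whose only codes are for constipation.

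**The concern.** The extent of off-label use by indication is a primary research question (section 8.1). Severity cannot be coded, so being classed as IBS-C is in practice what separates on-label from off-label use in adults. The list of constipation codes that complete IBS-C therefore sets the UK result directly. It also decides who enters the IBS-C side of the Cox comparison of time to discontinuation or switching (section 9.7.2).

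The protocol gives two lists. The wider one includes a code that itself attributes the constipation to a drug. Such a record points towards a constipation disorder other than IBS-C, which is what the section 8.2 objective sets out to count. The narrower list leaves that code out, but it also leaves out functional and chronic constipation, and it does not say where the excluded users are then counted.

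**Working it through.** No sample size or power figure is involved. The check applies the printed rules to the codes and then to example users.

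**Step 1. Count the constipation codes in Table 4 by label.**

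| Label in Table 4 | Codes | Number |
|---|---|---|
| Preferred | 19C..11, 19C..00 | 2 |
| Second choice | J520.00 (functional) | 1 |
| Third choice | J520z00 | 1 |
| Infrequent | 19C2.00, 19CZ.00, J520100, J520000, J520200, J520300, E264500, J520y00 | 8 |

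Total: 2 + 1 + 1 + 8 = 12, all marked for combination with IBS.

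**Step 2. State the two readings.**

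- Reading A (Table 4 comments with section 9.3.4): any of the 12 codes completes IBS-C.
- Reading B (criterion under Table 4): only the 2 preferred codes do; 12 − 2 = 10 do not.

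**Step 3. Classify adult UK users with IBS code J521.00 and no diarrhoea code.**

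| Only constipation code | Reading A | Reading B |
|---|---|---|
| 19C..00 | IBS-C | IBS-C |
| J520300 (drug-induced) | IBS-C | IBS-M |
| J520000 (acute) | IBS-C | IBS-M |
| J520.00 (functional) | IBS-C | IBS-M |
| J520100 or J520200 (chronic) | IBS-C | IBS-M |

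IBS-M under reading B follows from the residual rule. It assumes that a user with IBS and a non-qualifying constipation code is treated as having IBS only, because no other class is offered.

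**Step 4. Find the section 9.7.1 subgroup under reading B.**

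- Constipation codes only: none of these users qualifies, because each has an IBS code.
- Non-IBS-C with chronic constipation: users with J520100 or J520200 plausibly qualify. Those with only J520300 or J520000 are not clearly included, since neither code shows chronic constipation.

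A user with IBS and a chronic constipation code can thus be on-label under A and in an off-label subgroup under B. A user with IBS and drug-induced constipation is on-label under A and has no clear place in either constipation subgroup under B.

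**Step 5. Mark the boundaries.** The conflict does not reach every user with an IBS code. J521000 is an exclusion code. A diarrhoea code leads to IBS-D, or to IBS-M if both sets of criteria are met. A user whose only IBS code is 14CF.00 is IBS-C as printed, whatever the constipation code. The ICD-10 rule under Table 5 uses a single constipation entry, K59.0, so this conflict does not arise there.

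**Step 6. Trace the effect on pooled results.** Section 4.9 plans aggregated analyses for the primary objectives. The projected UK share in section 9.5 is 2,674 / 9,665 = 27.7%. If that mix held, a shift of *d* percentage points in the UK would move the pooled percentage by about 0.28 × *d*. The protocol gives no basis for a value of *d*.

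**The case against.** The best defence is that the specific rule governs the general one. Section 9.3.4 speaks of potential cases and describes the annex tables as broad lists of varying specificity; the criterion under Table 4 is the operational definition. On that view neither J520300 nor J520000 completes IBS-C. This carries weight. A reader might infer that the plan counts users with drug-induced constipation as on-label, but that is only one of two readings, and arguably the weaker one.

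The defence does not remove the conflict. If only two codes count, the instruction to combine the other ten with IBS has no function, and neither does their ranking as second or third choice. A programmer could defend either version.

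A reader might also infer that the off-label constipation group loses these patients and that deleting the two codes would restore them. Steps 3 and 4 show otherwise. Under the narrower rule the deletion changes no one's class. Under the wider rule it would leave ten codes eligible against two in the criterion, and would still not place the users in a section 9.7.1 subgroup.

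It is also fair to say that the choice of codes is a matter of clinical coding judgement. Section 7 describes IBS as chronic and relapsing, so a recorded acute episode is compatible with IBS-C. That is a reason to decide J520000 explicitly rather than to presume it should go. It applies less to J520300, where the code names a different cause.

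Finally, section 9.9 accepts that IBS-C and chronic constipation are hard to separate. That concerns the limits of the data; two conflicting rules in one protocol are avoidable.

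**Conclusion.** The point holds as an internal contradiction in the UK definition of IBS-C: 12 eligible constipation codes by one text, two by another. It affects the UK on-label and off-label percentages, any pooled figure that includes the UK, and the IBS-C group in the Cox comparison.

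The size cannot be derived, because Table 4 gives no frequencies. For the drug-induced and acute codes alone it is probably small: both are labelled infrequent, and section 9.3.2 searches the whole medical history for prior diagnoses, so they will less often be a patient's only constipation codes. The effect of all ten disputed codes could be larger, since they include functional constipation (second choice) and the chronic constipation codes.

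The conclusion rests on the printed text alone. The statistical analysis plan was not available and may fix one reading; the protocol would still need to agree with it. This is a minor point, worth correcting because the correction is cheap and the affected figure is a primary one.

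**What to change.** 1. Replace the Table 4 comments, the section 9.3.4 wording and the criterion under Table 4 with one explicit list of the Read codes for constipation that complete IBS-C, used identically in all three places.
2. Leave J520300 off that list, so that drug-induced constipation alone does not complete IBS-C. A user who also has a qualifying constipation code is unaffected.
3. State whether J520000 counts, or include and exclude it in a sensitivity analysis. State the position of the functional and chronic constipation codes, which the narrower criterion now drops without comment.
4. In section 9.7.1, say where IBS users with only non-qualifying constipation codes are counted for the section 8.2 objective on other constipation disorders, so that they do not pass into IBS-M by default.

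The cost is a code-list edit in Annex 3.A, one sentence each in sections 9.3.4 and 9.7.1, and one further run if the sensitivity analysis is chosen. No new data are needed. Some UK users may change class, depending on which reading has been programmed.

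### The UK code rule labels patients with only a history-of-IBS code (14CF.00) as IBS-C without a constipation code, which contradicts the protocol's own IBS-C and IBS-M rules

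*Protocol*

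**What the plan says.** Section 9.3.4 of the protocol explains why subtype has to be built from several codes: "There are several Read, ICD-9 or ICD-10 codes related to IBS, but none are specific to IBS-C". To identify potential IBS-C, "a combination of an IBS code with a code for constipation will be used". The same section names the indication: "The target indication of linaclotide is the treatment of moderate to severe IBS-C in adults".

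Annex 3.A turns this into rules for the UK Read codes. Table 4 describes 14CF.00 and its purpose as "History of irritable bowel syndrome (IBS) To identify potential prevalent cases". The rules below the table then run in this order:

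1. A patient has IBS with "One or more IBS- related codes among the following: J521.00, J521.11, J521.13, Eu45324, 14CF.00". A combination of symptom codes is an alternative route.
2. "Patients with only 14CF.00 will identify as prevalent IBS-C patients since the diagnosis date is uncertain".
3. IBS-C is defined as "Patient with IBS as specified above and one preferred code including the term “constipation".
4. IBS with a diarrhoea code is IBS-D, and "Patients with IBS only or meeting both criteria will be IBS-M".

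For Spain and Sweden, the ICD-10 rules in the same annex place IBS that meets neither the IBS-C nor the IBS-D criteria in IBS-M. The ICD-9 rules place the IBS code without constipation or diarrhoea codes in IBS-M.

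**The concern.** Rule 2 gives the constipation subtype to patients with no recorded evidence of constipation. Its stated reason, an uncertain diagnosis date, bears on whether a case is prevalent or incident and not on bowel habit. The result is out of order: a history code alone yields IBS-C, while a full IBS code alone, such as J521.00, yields IBS-M.

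The label matters in two places. IBS diagnosis and type is a baseline variable, with the IBS-C proportion to be given where possible (section 9.3.2 and its footnote). IBS-C versus other is also the contrast in the last objective of section 8.2 and in the Cox models of section 9.7.2. An analyst coding the annex has to choose between two labels, and that choice changes both outputs. It also makes the UK rule differ from the ICD-based rules, although section 4.9 plans analyses aggregated over the three countries for the primary objectives.

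**Working it through.** The plan states no figure on this point, so there is none to reproduce. The check applies the UK rules in Annex 3.A to small sets of codes, using 19C..00 as a preferred constipation code and 19F.. as a diarrhoea code.

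| Codes on record | 14CF.00 sentence | IBS-C rule (IBS + preferred constipation code) | IBS-D / IBS-M rules | Result |
|---|---|---|---|---|
| 14CF.00 | IBS-C | not met | IBS only, so IBS-M | **IBS-C and IBS-M** |
| J521.11 | does not apply | not met | IBS only, so IBS-M | IBS-M |
| 14CF.00 + 19C..00 | does not apply | met | not met | IBS-C |
| 14CF.00 + 19F.. | does not apply | not met | IBS-D | IBS-D |
| J521.11 + 19C..00 | does not apply | met | not met | IBS-C |

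Only the first row is inconsistent. The table takes the sentence to mean that 14CF.00 is the patient's only relevant code. If it means that 14CF.00 is the only *IBS* code, the fourth row also conflicts: IBS-C by the sentence and IBS-D by the diarrhoea rule.

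**Which sentence is out of line.** Section 9.3.4 needs two codes for IBS-C, and a single code cannot supply them. Table 4 gives 14CF.00 the purpose of finding prevalent cases and does not mention constipation. The feasibility text on the UK database in Annex 3.B also says that patients are classified by code combinations. The ICD-10 and ICD-9 rules send untyped IBS to IBS-M. All of these agree with one another and disagree with the 14CF.00 sentence.

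**Effect on the listed off-label groups.** Sections 8.2 and 9.7.1 list constipation other than IBS-C, codes for constipation only, paediatric chronic constipation, eating disorders, and low body mass index. A patient whose only relevant code is 14CF.00 has no constipation code and so enters none of the constipation-based groups under either label. The remaining groups do not depend on IBS subtype. No listed count changes.

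**Size.** Let *f* be the share of UK users with only 14CF.00 and *p* the share meeting the two-code IBS-C rule. The documents give neither, so the values below are assumptions. The base is the 2,674 UK users projected in Table 3.

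- Users moved into IBS-C = 2,674 × *f*. For *f* = 1%, 2%, 5% and 10% this is 27, 53, 134 and 267.
- The UK IBS-C proportion rises from *p* to *p* + *f*, that is, by *f* itself.
- Share of the IBS-C group with no constipation code = *f* / (*p* + *f*). With *p* = 50% and *f* = 1%: 0.01 / 0.51 = 2.0%. With *p* = 30% and *f* = 10%: 0.10 / 0.40 = 25%.

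These lines show how the effect scales. They do not estimate it.

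**The case against.** The strongest reply is that this is a drafting slip. Given Table 4 and the stated reason, the authors probably meant prevalent IBS, or meant patients whose only IBS code is 14CF.00 and who also meet the constipation rule. That is likely, but the text says neither, and the annex is what will be programmed. It is a reason for the correction.

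A second reply is that few patients may be affected. This stands. Section 9.3.2 searches the entire medical history for prior diagnoses, so an affected user must never have had J521.00, J521.11, J521.13 or Eu45324, nor a preferred constipation code. The base is uncertain too: section 9.5 reports that actual users were below the targeted numbers, and the title of Table 3 describes the projected users as IBS-C patients.

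A third reply is that section 9.9 already expects misclassification between subtypes. That caveat covers imperfect recording in the databases. It does not cover a written rule that conflicts with its neighbours.

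Two stronger readings are tempting. A reader might infer that UK off-label use is understated by the share of patients with only 14CF.00. That would hold only if off-label were defined as everyone who is not IBS-C. The broad question in section 8.1 leaves room for such a definition, but the protocol does not adopt it, and the listed groups do not move. A reader might also infer that the rule dilutes the IBS-C versus other contrast. That assumes these patients do not have IBS-C. With no code specific to IBS-C, a linaclotide user with an untyped IBS history may well have it, and IBS-M is also an assigned label. The direction of any bias is not shown.

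**Conclusion.** The contradiction holds on the current wording. Annex 3.A gives a UK user with only 14CF.00 both IBS-C and IBS-M, and the 14CF.00 sentence is the one that departs from section 9.3.4, from the adjacent rules and from the ICD rules. Applied literally, it raises the UK IBS-C proportion by exactly the share of such users and places them in the IBS-C group of the discontinuation and switching comparison. That share is unknown and may be close to zero. The finding is limited to the UK data. It shows neither a biased off-label percentage nor a biased hazard ratio. It is worth correcting because the rule is fixed in the protocol, feeds reported results and costs almost nothing to repair.

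**What to change.** Replace the 14CF.00 sentence in Annex 3.A with wording to this effect: *A patient whose only IBS code is 14CF.00 is recorded as a prevalent IBS patient, because the date of diagnosis is uncertain; the subtype is then set by the constipation and diarrhoea rules that follow.*

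Under this wording 14CF.00 alone becomes IBS-M, as J521.00 alone already is. With a preferred constipation code it stays IBS-C, and with a diarrhoea code it stays IBS-D. Every record in the table above then has one label. A new class for IBS without a recorded subtype should not be added through this sentence alone, because it would conflict with the IBS-M rule unless that rule were changed too.

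Also report the number of UK users whose IBS status rests on 14CF.00 alone, so that the reader can see how much depends on the rule. If the sponsor does intend an exception for these patients, the annex should say that it overrides the other rules, give a reason that concerns constipation, and plan a sensitivity analysis without it.

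The cost is one sentence in the annex, one line in the classification program and one reported count. No new data are needed, and no sample-size figure changes.
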